#### **9.4.5 Covariates**

Due to the non - interventional nature and design of the observational study, this registry does not require diagnostic/therapeutic procedures or strict timeline visit schedule. Patients will receive treatment according to standard clinical practice with regards to visit frequencies, type of performed assessments and according to local prescription requirements.

Following identification of a potential patient, the investigator will follow the below listed procedures:

1. Review of individual patient's medical history, to confirm that the inclusion/exclusion criteria are met.
2. Explanation of the study objectives to the patient and receipt of signed and dated informed consent, after providing the patient with sufficient time to read carefully and understand the information sheet.
3. Data collection from the medical records of eligible for enrollment patients, as required by eCRF, and eCRF completion.

Please refer to [Section 11.2](#) for details regarding Adverse Event and Serious Adverse Event Collection and Reporting.

A tabulated schedule of assessments that provide information regarding the recommended timeline of data collection and represents the standard clinical care of IPF treated patients is listed below in [Table 1](#). The exact definitions of the variables can be found in Appendixes 2-5.

Table 1. List of variables to be documented (if available) at scheduled visits

Variable (Please refer to Annex 4 )	Assessment	Follow up**
Eligibility criteria	x	
Baseline information (assessment)		
(Socio-)demographic variables: age, gender, race, height, index employment status, insurance status	x	
Weight, blood pressure, heart rate	x	x
(Possible) IPF risk factors		
Cigarette smoking incl. pack years (Categorized as never/past/current/unknown. For past/current, specify packs/year and for past, number of years smoking one pack per day); environmental and occupational exposure; alcohol and substance abuse; exposure to drugs associated with IPF ; exposure to viral infection possibly related to IPF; gastro-oesophageal reflux; genetic factors (family history); others	x	
Co-morbidities (Please refer to Annex 5 )	x	x
IPF		
Baseline information (assessment) on IPF		
First symptoms; date of first diagnosis, dates and results of HRCT, surgical lung biopsy, bronchoalveolar lavage.	x	
Symptoms		

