## **9.5 DATA SOURCES**

The study will mainly include the recording of new data through a web based system for data collection. Data will be collected by the study doctors as they occur according to standard clinical practice in the approximate visiting schedule indicated above.

Source (primary) patient data related to their medical and IPF history will be collected by the investigators from the patient's medical files/records and will be documented in the relevant eCRF section.

Data regarding treatment modifications, concomitant treatments, study related routine clinical assessments, adverse events (ADRs) and survival status will also be collected. If a patient withdraws early from the study, they will be contacted via telephone at the end of the Study in order to evaluate their survival status. Another follow-up assessment should be performed if possible (unless reason for discontinuation is erroneous enrolment of the patient into the study at baseline), and data should be entered on the eCRF of the next planned visit unless the patient has actively withdrawn consent for any kind of future contacts.

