## 9.7 DATA MANAGEMENT

The registry will include the collection of new data that will be recorded in an existing web based database in a consecutive manner (electronic case report form, eCRF) as well as transferring already existing data to the system from medical charts. The patients will be identified by subject identification number, site number, and study identification number.

Investigators will enter the data of their patients directly into an internet-based electronic case record form. At data entry, plausibility checks (e.g., range checks, conditional checks, etc.) will be performed. Data will be entered in the eCRF system by the study personnel at the Investigator's site, according to the Investigator Instructions Manual. Data entered in the eCRF system will be automatically saved to a central database and changes tracked to provide an audit trail. When data have been entered, reviewed and edited, the Investigator shall sign the e-CRF electronically as per the agreed project process and data will be locked to prevent further editing.

Query management will be performed through built-in query management functionality that will be incorporated into the eCRF.

Prior to the onset of data management activities, a detailed data management plan (DMP) will be issued describing the procedure to be followed for processing all collected study data in order to ensure they are valid, complete and accurate for statistical analysis. In addition, aiming at ensuring the expected quality of data, a thorough data cleaning session will be applied. When all data have been properly validated and the quality control procedure has been completed, a declaration of database lock will take place so that it can be confirmed that all important actions have been properly performed. In addition, prior to database lock, and prior to the initiation of any statistical analysis activities a comprehensive statistical analysis plan (SAP) will be drafted. The SAP will also include information regarding the statistical software(s) to be used for the analysis of the study data and any data imputation methods that may be applied.

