## **5. ENDPOINTS(S)**

### **5.1 PRIMARY ENDPOINT(S)**

The main objective of this IPF registry is to gain further knowledge on the characteristics, management, progression and outcomes of patients with IPF as treated under real-world, clinical practice conditions in Greece.

More specifically, this registry is going to:

- Provide a comprehensive clinical picture for IPF
- Track access to health care and cost of caring for IPF patients over time
- Examine the implementation of treatment guidelines, used on patients diagnosed with IPF, according to the existing diagnosis guidelines
- Characterize patients on different treatments.

Endpoints are targeting the description of the following:

- Demographic data including age, gender and race, employment status and insurance status.
- Change from baseline in vital signs as measured at 3,6,12,18 and 24 months following to the baseline visit.
- Vital Status.
- Cardiopulmonary exercise testing (6-minute walk distance and CPET, if performed)
- Change from baseline in 6-minute walk distance VO2max (CPET) as measured at 3,6,12,18 and 24 months following to the baseline visit.
- IPF risk factors as measured at baseline visit: (cigarette smoking including pack years, alcohol and substance abuse, environmental and occupational exposure, exposure to drugs associated with IPF, exposure to viral infection possibly related to IPF, gastro - oesophageal reflux, genetic factors - family history).
- Description of the comorbidities throughout the trial.
- Risk of bleeding and thrombosis as stated in the CRF.
- Description of the newly diagnosed patients of acute respiratory worsening, exacerbations, and hospitalization due to any cause and due to IPF.
- Description of the intensity of treatment, frequencies and resource utilization for pharmaco-economic analyses.
- Description of methods and procedures used in the diagnosis of IPF and time since diagnosis.
- Description of IPF symptoms (dyspnea, cough, weight loss, fatigue, dizziness, chest pain, anxiety, clubbing, bibasilar crackles)

- Description of autoimmune biomarker.
- Description of lung function and/or exercise capacity.
- Description of IPF treatment modalities.
- Description of Physician's clinical rating of the probable course of IPF (stable, slow or rapid progression).

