## **6.7 BASELINE, TIME WINDOWS AND CALCULATED VISITS**

No visit windows will be used. The CRF nominal visits will be applied for the analysis. Unscheduled visits are not expected and if any they will not be counted for primary and secondary endpoints. However, they will be considered for the safety analysis regarding Adverse Events (if any).

The baseline value will be the first measurement made after the enrolment to the study.

Baseline information will be presented appropriately in the “by visit” summaries.

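### SAP 6.7 allows a follow-up value to serve as baseline, so changes from baseline can cover a shorter span than their visit label implies

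*SAP*

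**What the plan says.** SAP 6.7 gives one rule: "The baseline value will be the first measurement made after the enrolment to the study". There is no outer time limit, no role for a value obtained before enrolment, and no statement that a follow-up value is ineligible. The same section adds: "No visit windows will be used. The CRF nominal visits will be applied for the analysis".

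The change endpoints are counted from the baseline visit. SAP 5.1 lists "Change from baseline in 6-minute walk distance VO2max (CPET) as measured at 3,6,12,18 and 24 months following to the baseline visit" and words the vital-signs endpoint in the same way. SAP 7.8.2 (laboratory data) and 7.8.3 (vital signs) compute change at each visit as the post-baseline value minus the baseline value. Lung function appears in SAP 5.1 only as something to be described. SAP 7 has the recorded baseline visit analysed on its own, and SAP 6.6 rules out imputation.

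On how values arise, Protocol 9.4.5 says that "this registry does not require diagnostic/therapeutic procedures or strict timeline visit schedule", and Table 1 is headed "List of variables to be documented (if available) at scheduled visits". The step after consent is "Data collection from the medical records of eligible for enrollment patients, as required by eCRF, and eCRF completion". Protocol 9.7 describes collecting new data "as well as transferring already existing data to the system from medical charts". Protocol 9.5 sets the balance: "The study will mainly include the recording of new data through a web based system for data collection". It assigns the medical files to the patient's medical and IPF history.

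**The concern.** A first-value-after-enrolment rule is harmless when every patient is measured at entry. Here that is not assured, because a test is recorded only if routine care produced it. Two kinds of patient are exposed:

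- those with no measurement at the entry visit;
- those whose baseline page holds only a value obtained before consent, for example at the diagnostic work-up. Read literally, SAP 6.7 disqualifies that value.

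In both cases the first eligible value may come from month 3, 6 or 12. Every later change is then measured from that point but still labelled by months since the baseline visit, so the summary mixes different spans under one label. Disease progression is part of the main objective, and for a measure that falls steadily the mixing understates decline. The baseline table and the change tables could also use different baselines for the same patient.

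**Working it through.** **No plan figure to reproduce.** Neither document gives the share of patients without an entry-visit value or the expected size of any change. Protocol Table 2 concerns the precision of proportions and is not an input here.

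**Inputs.** Follow-up visits at 3, 6, 12, 18 and 24 months (Protocol 9.3.3); the baseline rule (SAP 6.7); change equals post-baseline minus baseline (SAP 7.8.2, 7.8.3). Assumptions: linear decline of d per month, the same in all patients; a share m of patients whose first post-enrolment value is at month b; m between 10% and 50%.

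**One affected patient.** Change from entry to month t is −d·t. Measured from month b it is −d·(t − b). The fraction lost is b/t.

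| Baseline taken at | Lost at month 6 | Lost at month 12 | Lost at month 24 |
|---|---|---|---|
| month 3 | 3/6 = 50% | 3/12 = 25% | 3/24 = 12.5% |
| month 6 | – | 6/12 = 50% | 6/24 = 25% |
| month 12 | – | – | 12/24 = 50% |

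For example, take a patient whose walk test was done shortly before consent, with further tests only at months 6 and 24. The month-6 test becomes baseline, and the change labelled month 24 covers 24 − 6 = 18 months.

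**Whole cohort.** Mean change becomes −d·(t − m·b), so the shortfall is m·b/t.

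| Baseline taken at | Month 6 | Month 12 | Month 24 |
|---|---|---|---|
| month 3, m = 10–50% | 5–25% | 2.5–12.5% | 1.25–6.25% |
| month 6, m = 10–50% | – | 5–25% | 2.5–12.5% |
| month 12, m = 10–50% | – | – | 5–25% |

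Check for b = 6 at month 12: 0.10 × 6/12 = 5% and 0.50 × 6/12 = 25%.

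The visit that supplies the baseline (t = b) is left out. Whether it yields a zero or no change value depends on programming.

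**After the fix.** If no follow-up value can be baseline, the shortfall from this source is 0. Patients without a baseline-visit value drop out of the change summary.

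**The case against.** The strongest reply is that SAP 6.7 should be read with its surroundings. Nominal CRF visits are used, change is counted from the baseline visit, that visit is analysed separately, and nothing is imputed. On that reading, baseline is the entry-visit value and a missing one stays missing. This is plausible and may be what was intended. But no SAP text makes it override the explicit sentence, and two programmers could produce different tables from the same data.

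Several stronger inferences are tempting and are not supported:

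- *That decline from entry is erased.* Only the stretch between entry and the substituted value is lost, and only in affected patients.
- *That a pre-consent test is the usual baseline record.* Protocol 9.5 says the data are mainly new. Chart transfer is provided for, but no share is given.
- *That affected patients get a change of exactly zero.* Under the SAP's formula the value serving as baseline need not also count as post-baseline, so that cell may be empty. The shortened later spans remain either way.
- *That the error always favours stability.* This needs steady decline, for which the documents give no basis in blood pressure, heart rate, ALT or bilirubin.
- *That FVC change is distorted.* The SAP names no lung-function change endpoint.

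It is also fair to say that the study is descriptive. Absolute laboratory and vital-sign values are shown at each visit, and survival, exacerbations and hospitalisations do not depend on this definition.

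**Conclusion.** The point holds as a defect in a stated rule. Followed literally, SAP 6.7 can discard a recent pre-consent value on the baseline page and let a month-3 or later value become baseline, and it fits poorly with the nominal-visit wording beside it and with SAP 5.1 and SAP 7. It affects change in vital signs, 6-minute walk distance, VO2max and laboratory values.

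The per-patient loss of b/t follows from linear decline alone. The cohort figures also need m, which is assumed. They run from 1.25% (month-3 baseline, m = 10%, month 24) to 25% at the visits tabulated, so the effect may be small if most patients are measured at entry. The plan should be corrected because the correction is nearly free, not because a large bias has been shown.

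**What to change.** Replace the baseline sentence in SAP 6.7 with wording to this effect: *Baseline is the value recorded at the nominal baseline visit (baseline eCRF page), including a value transferred from records to that page. A value first obtained at a follow-up visit is never used as baseline. If no baseline value exists, change from baseline is missing.* Report the number of patients without a baseline for each variable.

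Where test dates are collected, also report the time from test to baseline visit. Protocol Annex 4 lists dates for laboratory values, vital signs and lung function but has no entry for the walk test or CPET, so for those two the baseline page itself must define baseline.

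Any look-back limit is the sponsor's choice and carries an opposite error. Under the same linear assumption, a value taken k months before the visit overstates change at month t by k/t. With k = 3 that is 3/3 = 100% at month 3, 3/6 = 50% at month 6 and 3/12 = 25% at month 12.

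The cost is one SAP paragraph and a small programming change, with no new data collection. Some patients lose a change value, but that value did not measure change from entry.

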## **7. PLANNED ANALYSIS**

Continuous variables will be listed as mean value with standard deviation (SD) and median, along with minimum and maximum values (depending on the underlying distribution). The minimum and maximum values will have the precision of the data reported; mean, median values will have one additional decimal, whereas SD will have two additional decimals.

Categorical values will be listed as absolute and relative frequencies. Tabulations of frequencies for categorical data will include all possible categories and will display the number of observations in a category as well as the percentage (%) relative to the respective group (unless otherwise specified, all subjects in the respective subject set whether they have non-missing values or not). The precision for percentages should be one decimal point, unless the denominator is smaller than 100 (in all treatment columns), in which case percentages are given in integer numbers.

As soon as all patients are recruited and have the baseline visit recorded, then this visit will be analyzed. The information to be reported is shown at the corresponding revised display plan of the study, dated 24 April 2020.

### **7.1 DEMOGRAPHIC AND OTHER BASELINE CHARACTERISTICS**

Only descriptive statistics are planned to be performed.

### **7.2 CONCOMITANT DISEASES AND MEDICATION**

As concomitant medication is considered any treatment received after the enrollment to the study. Concomitant medication will be presented according to the CRF order.

Any comorbidity reported which started prior to the study enrollment will be summarized as medical history. Separate table will summarize all comorbidities started following to the participation to the study.

Only descriptive statistics are planned to be performed.

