Name of company: Boehringer Ingelheim			
Name of finished medicinal product: Not applicable			
Name of active ingredient: Not applicable			
Protocol date: 29 August 2016	Study number: 1199.252	Version/Revision: 1.10	Version/Revision date: 22 February 2018

• Age <math>\geq</math>40 years old at the time of inclusion

• Written informed consent for participation in the registry

• Patients that can be further followed up by the investigator, during the scheduled study period

 
Exclusion Criteria
 

• Expected lung transplantation within the following 6 months

 
Participation in clinical trials
			
Variables:	
At baseline, a relevant patient history will be recorded including IPF-related events up to 12 months prior to this visit. Further, the current status of IPF patients will be recorded regarding
 

• Basic (Socio-)demographic data

• Vital status

• Physical and vital signs examination

• Cardiopulmonary exercise testing (6-minute walk distance and CPET, if performed)

• IPF risk factors

• Co-morbidities

• Risk of bleeding and thrombosis

• Collection of pre-specified outcome data (only for newly diagnosed patients). Please, refer to Annex 3

• Recording of therapeutic regimens. Assessment of the intensity of treatment, frequencies and resource utilization for pharmacoeconomic analyses. Methods and procedures used in the diagnosis of IPF and date of diagnosis (including HRCT and SLB)

• IPF symptoms

• Biomarker results of autoimmune disease

• Assessment of function (lung function, cardiopulmonary exercise testing and/or exercise capacity if available)

• IPF treatment modalities

• Physician's clinical rating of the probable course of IPF (please refer to Table 1)

• Clinical events and hospitalizations

• Management of IPF and physician contacts

		

Name of company: Boehringer Ingelheim			
Name of finished medicinal product: Not applicable			
Name of active ingredient: Not applicable			
Protocol date: 29 August 2016	Study number: 1199.252	Version/Revision: 1.10	Version/Revision date: 22 February 2018

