## **ANNEX 5. COMMON COMORBIDITIES OF INTEREST (RECODER WITH START, AND IF APPLICABLE STOP DATE)**

- Previous Haemorrhages
- Cardio and cerebrovascular comorbidities: Arterial hypertension, coronary artery disease (CAD), myocardial infarction (MI), congestive heart failure (CHF), CNS Infarction, transient ischaemic attack (TIA), peripheral artery disease, atrial fibrillation, deep venous thrombosis, pulmonary embolism, pulmonary hypertension
- Respiratory comorbidities: chronic obstructive pulmonary disease (COPD), emphysema (radiologic), asthma, pneumonia, obstructive sleep apnea
- Renal comorbidities: chronic renal failure (see definition in Section 14.2)
- Hepatic comorbidities: chronic hepatic failure, cirrhosis
- Gastrointestinal comorbidities: gastroesophageal reflux disease (GERD), gastric ulcer, appendicitis, abdominal surgery, inflammatory bowel disease (e.g. Crohn's disease, ulcerative colitis), GI cancer, diverticulitis, superior mesenteric artery syndrome
- Metabolic comorbidities: T2/T1 diabetes mellitus, hyperlipidaemia, hypothyroidism
- Neoplasms: lung, liver, stomach, colorectal, breast and oesophageal, prostate and cervix cancer
- Depressive disorder, anxiety disorder.

**ANNEX 6. HIGH RESOLUTION COMPUTED TOMOGRAPHY  
CRITERIA FOR USUAL INTERSTITIAL PNEUMONIA  
PATTERN (UIP) [1]**

UIP Pattern (All Four Features)	Possible UIP Pattern (All Three Features)	Inconsistent with UIP Pattern (any of the Seven Features)
Subpleural, basal predominance  Reticular abnormality  Honeycombing with or without traction bronchiectasis  Absence of features listed as inconsistent with UP (see column 'Inconsistent with UIP Pattern', on the right)	Subpleural, basal predominance  Reticular abnormality  Absence of features listed as inconsistent with UP (see column 'Inconsistent with UIP Pattern', on the right)	Upper or mid-lung predominance  Peribronchovascular predominance  Extensive ground glass abnormality (extent>reticular abnormality)  Profuse micronodules (bilateral, predominantly upper lobes)  Discrete cysts (multiple, bilateral, away from areas of honeycombing)  Diffuse mosaic attenuation/air-trapping (bilateral in three or more lobes)  Consolidation in bronchopulmonary segment(s)/lobe(s)

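### SAP 7.2 sorts comorbidities by start date alone, so for conditions that can resolve the planned tables cannot show how many patients had them active at enrolment or during the study

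*SAP*

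**What the plan says.** SAP 7.2 gives two rules for comorbidities. The first is "Any comorbidity reported which started prior to the study enrollment will be summarized as medical history". The second is "Separate table will summarize all comorbidities started following to the participation to the study". Both depend on the start date. Neither mentions a stop date, and the SAP defines no category for a condition that is present at enrolment. The section adds that "Only descriptive statistics are planned to be performed".

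The tables serve an item that SAP 5.1 lists among the primary endpoints: "Description of the comorbidities throughout the trial". On the data side, the title of Protocol Annex 5 says how the comorbidities of interest are recorded: "RECODER WITH START, AND IF APPLICABLE STOP DATE". Protocol Table 1 marks co-morbidities at baseline and at follow-up. The Variables part of the Protocol abstract introduces its baseline list, which includes co-morbidities, with "Further, the current status of IPF patients will be recorded regarding".

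**The concern.** A description of comorbidities over the whole study should tell the reader how many patients had each condition when they entered and how many had it at some time while observed. A start-date rule does not deliver this for a condition that can end. A pneumonia that cleared years before entry and a depressive disorder still present at every visit get the same label in the same table. The second table cannot make up the difference, because it holds new onsets only.

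What is at stake is the reported comorbidity burden of the cohort, which is part of the comprehensive clinical picture that the registry sets out to give. The study is descriptive, so no hypothesis test, error rate or sample size depends on this.

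**Working it through.** The plan states no figure on this point, so there is none to reproduce. The check applies the SAP 7.2 rules to the possible date patterns and compares the result with what the endpoint needs.

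**Step 1: classify.** Start and stop dates are those of Annex 5.

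| Pattern | Start | Stop | Table under SAP 7.2 | Active at enrolment | Active during study |
|---|---|---|---|---|---|
| a | before enrolment | before enrolment | medical history | no | no |
| b | before enrolment | none, or on or after enrolment | medical history | yes | yes |
| c | after enrolment | any | new onset | no | yes |

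Patterns a and b differ in both right-hand columns but fall in the same table.

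**Step 2: count.** For one condition, let R, O and N be the numbers of patients in patterns a, b and c, each patient in one pattern only.

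- Planned output: history table H = R + O; new-onset table N.
- Needed: active at enrolment = O = H − R; active during the study = O + N.
- R is not reported. From the tables alone, O can be anything from 0 to H, and O + N anything from N to H + N.
- Adding the two tables gives H + N, the number who ever had the condition. This equals the number active during the study only if R = 0.

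A patient with one resolved episode before entry and another on study appears in both tables. The sum then counts that patient twice.

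**Step 3: size under stated assumptions.** The target of 300 patients is in Protocol 9.6. The other inputs are assumptions: mean follow-up 1.6 years, a share of patients with the condition before entry, and a yearly onset rate among the rest.

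- 10% with history, 2% onset: H = 0.10 × 300 = 30. N = 270 × (1 − exp(−0.02 × 1.6)) = 270 × 0.0315 = 8.5, about 9. Active at enrolment: 0 to 30 (0% to 10%). Active during the study: about 9 to 39 (8.5/300 = 2.8% to 38.5/300 = 12.8%).
- 50% with history, 3% onset: H = 150. N = 150 × (1 − exp(−0.03 × 1.6)) = 150 × 0.0469 = 7.0. Active at enrolment: 0 to 150 (0% to 50%). Active during the study: 7 to 157 (2.3% to 52.3%).

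The width of each range is H, whatever the onset rate. If the condition seldom resolves, R is near zero, the truth sits at the upper end, and the history count is close to enrolment prevalence. If most episodes resolve, it sits near the lower end.

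**Step 4: compare within the section.** SAP 7.2 treats drugs differently: "As concomitant medication is considered any treatment received after the enrollment to the study". A drug started before entry and continued counts as concomitant. A disease started before entry and continuing does not reach the on-study table. The SAP does not explain the difference.

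**The case against.** The strongest reply is that nothing is lost. Every comorbidity goes into one table or the other, and separating pre-existing from new conditions is a legitimate layout. That stands. A reader might infer from the rule that ongoing conditions disappear from the report. The documents do not support this: such conditions are in the history table, only not marked as ongoing.

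A reader might also infer that the on-study table misses most affected patients, because in the second example it shows 7 of 157. That comparison does not measure the defect. The 157 is 150 + 7, the sum of the two planned tables, so the ratio says only that new onsets are fewer than pre-existing cases. For a lasting condition the two tables together give the right total.

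It also stands that much of Annex 5 is little affected. Hypertension, COPD, diabetes and cirrhosis seldom resolve. Previous haemorrhage and abdominal surgery are history items by nature. Protocol Annex 3 defines several events separately as outcomes, including myocardial infarction, CNS infarction and deep vein thrombosis, and new occurrence is the relevant count there.

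Other parts of the SAP might be thought to close the gap. SAP 6.7 puts baseline information into by-visit summaries, and SAP 7.4 plans primary-endpoint summaries overall and by time of diagnosis. Neither adds a split by ongoing or resolved status. For the baseline-visit analysis, SAP 7 refers to another document: "The information to be reported is shown at the corresponding revised display plan of the study, dated 24 April 2020". That display plan is not among the documents reviewed and could contain a split, so the conclusion is about the SAP text and not about the tables as finally laid out.

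**Conclusion.** The point holds for conditions that can resolve. For these, SAP 7.2 as written yields ever-had and new-onset counts and cannot yield the number of patients with the condition active at enrolment or during the study, although SAP 5.1 makes comorbidity across the trial an endpoint. The documents do not allow the size to be fixed: the uncertainty equals the number of patients in the history table for that condition, and how much of it matters depends on the share already resolved. For conditions that seldom resolve the effect is small.

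Which conditions resolve is a general clinical assumption and is not stated in the plan. The conclusion also assumes that the display plan adds no split. This is a worthwhile and cheap improvement to descriptive reporting; it does not threaten the validity of the study.

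**What to change.** Rewrite the comorbidity rule in SAP 7.2 to use start and stop dates and report three groups per condition, overall and for newly and previously diagnosed patients:

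1. Resolved before enrolment: stop date before enrolment.
2. Ongoing at enrolment: started before enrolment, with no stop date or a stop date on or after enrolment.
3. New: started after enrolment.

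Report group 2 as baseline prevalence. Report patients in group 2 or 3, each counted once per condition, as comorbidities during the trial. The new-onset table can stay as it is.

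State two further rules. One assigns onset on the enrolment day, which the present wording leaves open. The other covers missing start or stop dates: SAP 6.6 sends significant dates to the sponsor's internal procedures without naming comorbidity dates.

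The cost is SAP wording and one extra table split, with no new data and no protocol change. The weak point is completeness: a stop date that was never entered looks the same as a condition that is still present and would be counted as ongoing, so stop dates should be queried before database lock. SAP version 2.0 is dated 13 May 2020 and data collection is planned to end on 5 June 2021, so the documented timeline leaves room for the change.
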